5 STUDY POPULATION

5.1 INCLUSION CRITERIA

1. Age 18 years or greater
2. Height between 5'2" and 6'2" (1.6 meters to 1.9 meters)
3. Weight less than 220 pounds (100 kilograms)
4. Near Normal range of motion (ROM), as follows: 1) Hip: more than 5 degrees of extension and 110 degrees of flexion; 2) Knee: Full extension to 110 degrees of flexion; 3) Ankle: at least 0 degree of dorsiflexion to 25 degrees of plantarflexion
5. Are eligible for locomotor training as part of inpatient rehabilitation
6. Independent with static sitting balance
7. Sufficient function upper extremity strength to manage walking aid (front-wheeled walker, platform walker, or crutches)
8. Able to follow directions

5.2 EXCLUSION CRITERIA

1. Uncontrolled cardiovascular conditions (i.e. heart failure, angina, hypertension)
2. Inability to sit upright due to orthostatic hypotension
3. Any form of progressive SCI as defined by the physician, such as cancers
4. Upper leg length discrepancy > 0.5" or lower leg discrepancy >0.75"
5. Skin integrity issues in areas that would contact the device or that would likely be made worse by device use
6. Pregnancy, colostomy, mechanical ventilation
7. Any other medical issue in the judgment of his/her clinicians that might prevent safe standing or walking
8. Non-English Speaking
9. Cognitive and/or communicative disability (e.g. due to brain injury). Participants must be able to follow directions well and demonstrate learning capability.

5.3 STRATEGIES FOR RECRUITMENT AND RETENTION

Prospective subjects will be recruited following admission to the AIR unit at Mount Sinai Hospital. Attending physicians and rehabilitation clinicians will identify patients admitted to the unit who may be eligible for the study. The informed consent process will be provided to interested and prospective

participants. Once the consent form is signed, a research team member and the study physician will begin the screening process for the inclusion/exclusion criteria.

6 STUDY INTERVENTION

6.1 STUDY INTERVENTION(S) ADMINISTRATION

6.1.1 STUDY INTERVENTION DESCRIPTION

Intervention (N=20): In the intervention group, participants will receive locomotor training provided with an Ekso™ powered exoskeleton according to the standard of care of AIR at Mount Sinai Hospital with the exception that the EAW training will be incorporated into the designated therapy times (3 hours of physical therapy (PT) and/or occupational therapy (OT)) which will be provided as determined by the clinical team from the earliest time they are identified to be able to safely stand, through discharge. The goal of EAW intervention is to complete three or more sessions of EAW training a week during the AIR period (after enrolling into the study until discharge). One EAW session is defined to have at least 20 minutes of uptime in the device (based on data output from EksoTM, device, not including donning and doffing time). EAW sessions will include device fitting, instruction for sit-to-stand and stand-to-sit maneuvers; balance and fall protection training; and walking on smooth indoor surfaces with total or variable device assistance. The clinical team will determine the frequency, duration, and intensity of each EAW session based on the participant's response to the previous session.

Control (N=10): In the control group, participants will receive standard of care AIR which includes three hours of PT and/or OT per day until they are discharged. This standard of care AIR may include bed mobility, balance, strength, gait, transfers, and wheelchair mobility training to improve participants' independence in activities of daily living, such as bathing, eating, dressing, grooming, and wheelchair use but does not include EAW. The two groups (control and intervention) will have the same total amount of therapy time.

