Study Population: Individuals with SCI who stay in the SCI acute inpatient rehabilitation

Phase: NA

Description of Sites/Facilities Enrolling Participants: Icahn School of Medicine at Mount Sinai

Description of Study Intervention: In the intervention group, participants will receive locomotor training provided with an Ekso™ powered exoskeleton. The EAW training will be incorporated into the designated therapy times (3 hours of physical therapy (PT) and/or occupational therapy (OT)).

Study Duration: 3 years

Participant Duration: Twenty to thirty minute per session, one session a day, equal or more than 3 sessions/days per week, from enrollment in the study to discharge from the acute inpatient rehabilitation. Different participants have different duration of participation based on their length of inpatient stay.

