6.2 MEASURES TO MINIMIZE BIAS: RANDOMIZATION AND BLINDING

Eligible participants will be randomized into either the intervention group or the control group. In order to provide more opportunities for participants to accept EAW training, the intervention group will have 20 participants, and the control group will have 10 participants.

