9 STATISTICAL CONSIDERATIONS

9.1 SAMPLE SIZE DETERMINATION

All statistical tests will be 2-sided. The outcome measures will be tested at a 0.05 level of significance. SPSS will be used to conduct the statistical analyses. All participants who have EAW sessions will be included (regardless of the number of sessions they complete before discharge, but the number and reason of missing EAW sessions will be recorded). To test the three main hypotheses of the proposed study, the change score of each outcome between baseline and discharge will be calculated. The change score will be compared between the intervention and control groups using independent t-test analyses (if the outcomes are not normally distributed, Mann-Whitney tests will be used).

Since the primary aim of the study is to compare the improvement of FIM scores between the groups, the FIM score results from the preliminary data were used to perform the power analysis for this study. In the preliminary data, the mean change in FIM score from the intervention group was 35 ± 12 , and the control group was 22 ± 13 . The effect size of the FIM score change in our preliminary data was 1.07 (controlling for the different number of participants between the two groups). The power analysis showed that using the effect size (1.07) and 0.05 level of significance with two-sided analysis in independent t-test, a total of 30 participants will provide the study 80% power.

To account for an expected attrition rate of about 25%, 40 participants will be enrolled. It is expected that 30 participants will complete the study (the reasons and number of screening failures and dropouts will be recorded).

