9.2 STATISTICAL ANALYSES

9.2.1 GENERAL APPROACH

All statistical tests will be 2-sided. The outcome measures will be tested at a 0.05 level of significance. SPSS will be used to conduct the statistical analyses. All participants who have EAW sessions will be included (regardless of the number of sessions they complete before discharge, but the number and reason of missing EAW sessions will be recorded). To test the three main hypotheses of the proposed study, the change score of each outcome between baseline and discharge will be calculated. The change score will be compared between the intervention and control groups using independent t-test analyses (if the outcomes are not normally distributed, Mann-Whitney tests will be used).

In addition to the primary analysis, several secondary analyses will be performed. 1) Each of the outcomes will be compared between pre- and post-EAW training using a paired t-test analysis (if the outcomes are not normally distributed, Wilcoxon signed-rank test will be used). 2) Analyses will be performed to determine the relationships between the change of outcome measures and EAW training time (including sessions, up time, walking time, or total number of steps per session and across all sessions) using correlation coefficients, regression analyses (stepwise and logistic), analyses of covariance, and nonparametric analyses as appropriate. 3) An additional exploratory post

hoc analyses will be to determine the relationship of participant's baseline characteristics with successful use of the exoskeleton. This post hoc analysis would serve as pilot data to begin to determine who is a good candidate for EAW training during AIR for a future study.

References:

1. Simpson, L.A., et al., *The health and life priorities of individuals with spinal cord injury: a systematic review*. J Neurotrauma, 2012. **29**(8): p. 1548-55.
2. Ditunno, P.L., et al., *Who wants to walk? Preferences for recovery after SCI: a longitudinal and cross-sectional study*. Spinal Cord, 2008. **46**(7): p. 500-6.
3. Tate, D.G., C.Z. Kalpakjian, and M.B. Forchheimer, *Quality of life issues in individuals with spinal cord injury*. Arch Phys Med Rehabil, 2002. **83**(12 Suppl 2): p. S18-25.
4. [name], T.N. and K.T. Ragnarsson, *Pain after spinal cord injury*. Phys Med Rehabil Clin N Am, 2000. **11**(1): p. 157-68.

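### Randomisation follows eligibility alone while exoskeletal-assisted walking (EAW) waits for standing clearance, so few-session participants can dilute the contrast and zero-session participants appear to be dropped from the EAW arm only

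*Combined protocol and SAP*

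**What the plan says.** **Randomisation.** Section 6.2 gives one condition: "Eligible participants will be randomized into either the intervention group or the control group". The split is 20 EAW to 10 control.

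**Start of EAW.** Section 6.1.1 has the clinical team provide EAW "from the earliest time they are identified to be able to safely stand, through discharge". The synopsis (Participant Duration) describes sessions running "from enrollment in the study to discharge from the acute inpatient rehabilitation". The session goal in 6.1.1 also counts the period from enrolment to discharge. Three or more sessions a week is a goal; no minimum total is set.

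**Eligibility.** Several items bear on readiness. Inclusions 5 to 7 require eligibility for locomotor training, independent static sitting balance and enough arm strength for a walking aid. Exclusions 2 and 7 remove people who cannot sit upright because of orthostatic hypotension and those with a medical issue that might prevent safe standing or walking. No item requires that standing clearance has been given, and none concerns days left before discharge.

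**Analysis set.** Sections 9.1 and 9.2.1 carry the same sentence: participants who have EAW sessions are included "regardless of the number of sessions they complete before discharge", with missed sessions and their reasons recorded. EAW-arm participants with no session are not mentioned.

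**The concern.** If eligibility can come before standing clearance, a participant can be allocated to EAW and spend part or all of the remaining stay unable to receive it. Controls need no such clearance, so only the EAW arm loses exposure. Two different harms follow.

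- **Few sessions.** The participant is analysed as EAW with little of the treatment. The expected difference shrinks while the sample stays at 30.
- **No sessions.** Read literally, the participant leaves the analysis. The control-arm counterpart, who would also have been slow to stand, stays in. If such patients tend to recover less, the exclusion would favour EAW. The documents give no data on this, so the direction is a plausible inference and not a finding.

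**Working it through.** **1. Inputs, all from sections 6.2 and 9.1.** FIM change 35 ± 12 (EAW) and 22 ± 13 (control), so the difference is 35 − 22 = 13. The test is specified as "0.05 level of significance with two-sided analysis in independent t-test". The plan states: "The effect size of the FIM score change in our preliminary data was 1.07", and "a total of 30 participants will provide the study 80% power". Allocation is 20:10.

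**2. The plan's own figure.** For a two-sided t-test the noncentrality is d × √(n₁n₂/(n₁+n₂)).
- At 15:15: 1.07 × √(225/30) = 2.93, power 80.7%. The stated 80% reproduces for equal groups.
- At the planned 20:10: 1.07 × √(200/30) = 2.76, power 76.0%. Reaching 80% at 2:1 takes 33 (22:11).
- Enrolment: 30/(1 − 0.25) = 40, as stated.
- Simulating directly from 35 ± 12 and 22 ± 13 at 20:10 gives 74%. The scenarios below start from this figure. The shortfall from 80% comes from the allocation and the printed SDs, not from the present issue, but it means there is no reserve.

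**3. Few sessions: dilution.** Let q be the share of the 20 analysed EAW participants with too little exposure. The documents do not give q; 10% to 30% is assumed.
- If they gain nothing, the difference is 13(1 − q). If they keep half the effect, it is 13(1 − q/2).
- In the first case the EAW-arm variance becomes 144(1 − q) + 169q + 169q(1 − q). At q = 20% this is 115.2 + 33.8 + 27.0 = 176.0. The pooled SD is √((19 × 176.0 + 9 × 169)/28) = 13.2, d = 10.4/13.2 = 0.79, and noncentrality is 0.79 × 2.58 = 2.04. That is about equal to the critical t on 28 df (2.05), so power is close to one half.

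Simulated power (pooled t-test, two-sided 0.05):

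| q | Difference, no gain | Power, no gain | Difference, half gain | Power, half gain |
|---|---|---|---|---|
| 0% | 13.0 | 74% | 13.0 | 74% |
| 10% | 11.7 | 63% | 12.35 | 69% |
| 20% | 10.4 | 51% | 11.7 | 64% |
| 30% | 9.1 | 39% | 11.05 | 59% |

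Affected participants have SD 13 in the no-gain columns and SD 12 in the half-gain columns. Repeat runs and other SD choices move these by about a point.

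**4. No sessions: exclusion.** If such participants are dropped and d stays 1.07, exact power goes from 76% (20:10) to 74% (18:10) and 72% (16:10). The loss of power is small. The damage is to the comparison, because one arm is selected after randomisation and the other is not.

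**The case against.** The strongest case against runs as follows.

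- **Readiness is already screened.** Someone with a medical bar to safe standing is not eligible, so randomisation before EAW is possible should be uncommon. This stands in part. It limits how large q is likely to be, but no criterion requires clearance itself, and 6.1.1 still treats clearance as a separate, possibly later step.
- **The power losses are too pessimistic.** This stands. The no-gain columns are a worst case, q is unknown, and the preliminary 35 ± 12 may already include patients with variable exposure. Subtracting dilution again would then double-count it. The table shows scenarios, not forecasts.
- **Variable exposure is part of the question.** Sections 2.1 and 2.2 ask whether EAW is feasible within inpatient practice, and 9.2.1 plans analyses of outcome against training time. This is a fair reason not to restrict entry by expected stay. It is no reason to leave the analysis set undefined.
- **The inclusion sentence is not a full definition of the analysis set.** Controls have no EAW sessions and are plainly meant to be analysed. This stands, which is why exclusion of zero-session participants is called apparent.

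Two stronger readings are tempting. A reader might infer that participants with no EAW at all are analysed and dilute the effect; the inclusion sentence covers only those who have sessions. A reader might also infer that the plan is defective without a minimum remaining stay. The synopsis openly accepts that participation varies with length of stay, and such a rule would narrow both accrual and applicability at a single site.

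**Conclusion.** The point holds in limited form. Randomisation is not tied to the event that allows EAW to begin, the statements about when EAW starts do not agree, and the analysis sentence keeps low-exposure EAW participants while appearing to omit those with none. The first effect is dilution: between about 69% and 39% power across the assumed scenarios, against 74% with none affected. The second is a one-sided exclusion whose cost is bias of unknown size rather than power. Both rest on an unstated share of participants, and the dilution figures also assume that the preliminary effect reflects adequate exposure. The sponsor should make the change, but the documents do not show that the problem will be common.

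**What to change.** 1. **Reconcile** the synopsis, the provision rule in 6.1.1 and the session goal in 6.1.1 on when EAW starts. Which clinical start point is right is for the study team.
2. **Section 6.2:** if the standing trigger in 6.1.1 is retained, randomise once the clinical team has recorded it, for both arms. EAW cannot begin earlier under that rule, so no EAW time is lost.
3. **Sections 9.1 and 9.2.1:** replace the sentence on participants who have EAW sessions with analysis of all randomised participants by assigned arm, including those with zero sessions.
4. **Report** time from randomisation to first session, and session counts, for the EAW arm.

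**Cost.** An amendment and recorded dates for the standing trigger and randomisation. Some consented participants may never be randomised; they would draw on the 40 − 30 = 10 places allowed for attrition. Change is measured from admission, and pain, CRP and walking baselines are taken around enrolment, so a longer wait puts more recovery before allocation in both arms. The team should decide whether any baseline needs repeating.

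A minimum remaining stay is an option for the sponsor to weigh against accrual and applicability, not a required change.

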3 OBJECTIVES AND ENDPOINTS

OBJECTIVES	ENDPOINTS
Primary	
To determine the effects of AIR with EAW compared with AIR without EAW (same total therapy time) on the changes from admission to discharge in the International Standards for Neurological Classification of Spinal Cord Injury (ISNCSCI) upper and lower extremity motor scores, Functional Independence Measure (FIM) scores, and Spinal Cord Independence Measure (SCIM) scores as classified by clinicians.	ISNCSCI examination results FIM scores SCIM scores
Secondary	
To determine the effects of AIR with EAW compared to AIR without EAW on reducing pain using the International Spinal Cord Injury Basic Pain Data Set 2.0 (ISCIBPDS 2.0) measures where type of pain is classified with the Spinal Cord Injury Pain Instrument (SCIPI).	Intensity of pain
Tertiary/Exploratory	
To determine the effects of AIR with EAW compared with AIR without EAW on reducing a specific systemic inflammatory mediator (C reactive protein, CRP).	CRP results

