8 STUDY ASSESSMENTS AND PROCEDURES

8.1 EFFICACY ASSESSMENTS

Demographic data:

1. Age: age of patient in years
2. Sex: male (M) or female (F)
3. Race: race of patient
4. Diagnosis: primary diagnosis of the patient from medical chart (include level of injury from the International Standard for Neurological Classification of Spinal Cord Injury (ISNCSCI) examination and the completeness of injury from American Spinal Injury Association Impairment Scale (AIS)) at admission and discharge.
5. Date (or year) of injury: the date of getting the diagnosis
6. Admission date: the date that the patient starts acute inpatient rehabilitation
7. Discharge date: the date that the patient discharged

Pain scale: 1) International Spinal Cord Injury Basic Pain Data Set (ISCIBPDS) to identify pain locations, average intensity (over the past three days), and influence on daily activities. 2) Spinal Cord Injury Pain Instrument (SCIPI) to classify patients' neuropathic or nociceptive pain. ISCIBPDS and SCIPI will be performed on the enrollment and discharge dates. 3) Participants' current level of pain before and after walking training will be recorded in the walking session data form.

Walking session results include session date, total up time, total walk time, and total steps. If subjects can walk independently 10-meter walking test and Walking Index for Spinal Cord Injury II (WISCI II) will be tested. In the 10 MWT, the participant will be asked to walk 10 meters (without the exoskeleton) at their fastest, comfortable pace. The time to cover this distance will be timed with a stopwatch. The 20-item WISCI-II provides a rank-order rating of the ability of a person with SCI to walk 10 meters in relation to the severity of impairment. Ratings consider the amount of assistance and the types of assistive devices (e.g., leg braces) required to walk. Both the 10 MWT and WISCI II will be evaluated after enrollment (within 1-2 days) and before discharge from AIR (± 2 days).

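### Therapy time is matched per scheduled day only; equal total time is neither ensured nor verifiable as delivered in either arm

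*Combined protocol and SAP*

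**What the plan says.** Section 3 sets the primary contrast as AIR with EAW "compared with AIR without EAW (same total therapy time) on the changes from admission to discharge", and the synopsis (section 1.1) words it the same way. Section 6.1.1 repeats the property as a fact about the arms: "The two groups (control and intervention) will have the same total amount of therapy time".

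Section 6.1.1 also defines what is scheduled. Controls receive "standard of care AIR which includes three hours of PT and/or OT per day until they are discharged". In the intervention arm, EAW is placed inside the designated 3 hours and continues through discharge, so it replaces other therapy and does not add to it. The words per day are written only for controls. The synopsis adds: "Different participants have different duration of participation based on their length of inpatient stay".

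On records, section 8.1 says: "Walking session results include session date, total up time, total walk time, and total steps". Section 9.2.1 adds that "the number and reason of missing EAW sessions will be recorded". Section 8.1 also lists admission and discharge dates, not limited to one arm. No section lists delivered PT or OT minutes, or minutes of other gait training, for either arm.

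On analysis, section 9.2.1 compares change scores by t-test or Mann-Whitney test, with no summary of length of stay or therapy time. Its exposure analyses use EAW training time only.

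**The concern.** Equal total time is part of how the primary question is put. It is what would let the sponsor say that a difference in Functional Independence Measure (FIM) gain reflects the kind of therapy and not the amount. A fixed number of hours per day until discharge does not fix the total, because the total also depends on days stayed, and the plan neither equalises nor reports these.

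If EAW shortened or lengthened the stay, the randomised contrast would still estimate the effect of offering EAW on change to discharge. Part of that effect could then come through more or fewer days of rehabilitation, and it would no longer be an effect at equal total time. As written, the plan would report it as one. What is at stake is the stated interpretation of the primary result.

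**Working it through.** **The plan's own figures.** The plan gives no figure for length of stay, therapy days or delivered minutes. Its one computed figure is 30 participants for 80% power at an effect size of 1.07 (section 9.1). By exact t this gives 80.7% at 15:15 and 76.0% at the planned 20:10. That difference is a separate matter, and nothing below depends on it.

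**Inputs from the documents.**
- Therapy: 3 hours a day until discharge (6.1.1).
- Allocation: 20 and 10 (6.1.1, 6.2).
- EAW goal: at least 3 sessions a week, each with at least 20 minutes of up time (6.1.1). The synopsis gives 20 to 30 minutes per session.
- Preliminary FIM change: 35 ± 12 and 22 ± 13 (9.1).

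**Assumptions, not in the documents.** SD of stay 7, 14 or 21 days; 5 or 7 therapy days a week; a 30-day stay and linear FIM gain where stated.

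**Step 1: what fixes total time.** Total hours = 3 × therapy days. Totals are equal only if therapy days are equal. Randomisation balances days in expectation, unless allocation itself changes them.

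**Step 2: chance difference in mean stay.** SE = SD × √(1/20 + 1/10) = SD × 0.387. Hours = 3 × SE at 7 therapy days a week, and that × 5/7 at 5 days.

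| SD of stay (days) | SE of arm difference (days) | Hours, 5 days/week | Hours, 7 days/week |
|---|---|---|---|
| 7 | 2.7 | 5.8 | 8.1 |
| 14 | 5.4 | 11.6 | 16.3 |
| 21 | 8.1 | 17.4 | 24.4 |

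**Step 3: compare with the EAW exposure.** The minimum goal is 3 × 20 min = 1 hour a week. That is 1/15 = 6.7% of weekly therapy at 5 days, or 1/21 = 4.8% at 7 days. Over an assumed 30-day stay it is 30/7 × 1 = 4.3 hours. A 2-day difference in mean stay is 2 × 3 × 5/7 = 4.3 hours at 5 therapy days a week, the same amount. The goal is a minimum: five 30-minute sessions a week would be 2.5 hours, or 10.7 hours over 30 days.

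**Step 4: what this means for FIM.** At 22 points over 30 days, gain is 22/30 = 0.73 points a day. One SE of stay is then worth 0.733 × 2.71 = 2.0 points (SD 7) to 0.733 × 5.42 = 4.0 points (SD 14), against the planned difference of 35 − 22 = 13.

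The pooled SD of FIM change at 20:10 is √((19 × 12² + 9 × 13²)/28) = 12.3. The SE of the FIM difference is 12.3 × 0.387 = 4.8 points. The 2 to 4 points lie inside that SE. They are part of the between-patient variation that the test already counts, not an added bias.

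The linear conversion also strains at the upper end. At SD 14, stay would contribute 0.733 × 14 = 10.3 points of SD, or 10.3²/12.3², about 70% of the variance of FIM change. At SD 21 it would contribute 15.4 points, more than the whole SD, so no FIM figure is given there.

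**Step 5: what can be verified.** Admission and discharge dates give length of stay, hence nominal hours, in both arms. The walking-session data and the missed-session count describe EAW and walking only. They do not give total PT and OT minutes in the intervention arm any more than in the control arm. Up time excludes donning and doffing, so it does not show how much conventional therapy EAW displaced.

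**The case against.** The strongest reply is that total here means PT, OT and EAW added together within the 3 scheduled hours. On that reading the design does specify parity, because EAW sits inside the hours. This stands for planned daily time. It does not rescue the wording, because the objective ties equal total time to change over the whole period from admission to discharge, and nothing tells the reader that a daily total is meant.

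Several stronger readings are tempting, and the documents do not support them.

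- *The arms will receive unequal time.* Nothing shows this. Daily hours are matched as planned, and randomisation balances stay in expectation.
- *The claim cannot be checked at all.* Nominal hours can be compared from dates already collected. Only delivered time is out of reach.
- *The recording gap is special to controls.* Total PT and OT minutes are not described for either arm.
- *The primary comparison is biased through discharge timing.* Only raters are described as blinded, but the documents do not say how discharge is decided. An effect of allocation on stay is possible but conjectural.
- *Controls will use the exoskeleton.* Section 6.1.1 excludes EAW from control care. The inpatient comments in section 2.2 are background, and gait training in controls is part of the standard-of-care comparator.

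**Conclusion.** The point holds as a mismatch between claim and design. The plan matches scheduled daily time, states equal total time, and describes no record of delivered PT and OT time in either arm. A conclusion at equal total therapy time would be unsupported. The randomised comparison of change scores is not biased or invalidated by this, and no sample-size figure changes.

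The size depends on a length-of-stay SD that the documents do not give. Over 7 to 14 days, the chance SE of the arm difference is 2.7 to 5.4 days. That is 5.8 to 16.3 hours across 5 to 7 therapy days a week, against a minimum EAW goal of 1 hour a week. These figures show how easily cumulative hours can differ by an amount comparable with the EAW exposure itself. They do not predict that the hours will differ, and they should not be read as FIM points wrongly credited to EAW.

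**What to change.** 1. In sections 1.1, 3 and 6.1.1, replace the equal-total-time wording with *same scheduled therapy time per day (3 hours, including EAW)*. Confirm in 6.1.1 that the 3 hours are daily in the intervention arm too.
2. Report length of stay from randomisation to discharge by arm, with a confidence interval for the difference. The discharge date is already collected; the randomisation date is not in the section 8.1 list and should be added.
3. For both arms, abstract from existing therapy records the delivered PT and OT minutes, the gait or locomotor minutes, and any exoskeleton use. Report them by arm with confidence intervals.
4. Describe the primary result as the effect of AIR with EAW versus AIR without EAW at equal scheduled daily time, and state any difference in stay or delivered time beside it.
5. Label any analysis that adjusts for or divides by length of stay as exploratory, because stay arises after randomisation. FIM gain per AIR day is not suitable as a planned supportive analysis: its denominator could itself be affected by EAW, and it includes days before randomisation, since recruitment follows admission (section 5.3).

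The cost is a wording change and modest chart abstraction for 30 to 40 participants. The downside is a less favourable claim. Treatment, sample size and the primary test stay as they are.
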